#### Analytic Plan:

Descriptive characteristics were computed for all patients combined and separately by dexamethasone group assignment. Categorical variables were reported as proportions in percentage, and continuous level variables as means and standard deviations. Separate independent t-tests were used to assess differences by group for post-discharge outcomes of interest including days for symptoms to resolve. Separate binary logistic regression adjusting for age, gender and severity of exacerbation were conducted to assess group differences in post-discharge outcomes including patients who had a return visit for unresolved asthma symptoms (ED, primary care or urgent care), days to symptom resolution, any missed school days between discharge and follow-up, rates of vomiting, and side-effects (changes in appetite, insomnia, mood swings); odds ratios with 95% confidence intervals were reported. Similar analyses were conducted to compare events and side effects between Groups 1 and 2 by asthma severity, using an intention-to-treat approach. Based on our clinical experience, we based our a-priori sample size calculation on an estimated non-inferiority limit of 11% and a rate of 12% return for asthma for each group. With a power of 80% and alpha of 0.05, a minimum sample size of 216 (108 subjects per group) was determined. All statistical tests were two-tailed, and analyses conducted with SYSTAT 13 (SYSTAT Software, 2004).

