### Study Protocol:

Block randomization was used to generate a list to be used for subject assignment with a 1:1 ratio of allocation to the single dose group and the two dose group. Demographic information such as age, gender, race, duration of asthma symptoms, number of previous hospitalizations, and current medication was collected. Pertinent exam findings such as patient's vital signs, pulse oximetry, and PAS were also collected along with medications given in the ED.

Group 1 was given 0.6mg/kg (max 16mg) of dexamethasone orally in the emergency department. Group 2 was given the same dose in the emergency department, and then a prescription for a second dose was sent to their pharmacy to be filled and administered at home 24 hours later. We worked with a nearby 24-hour pharmacy to ensure medication availability; however, pharmacy preference was left up to the family. Both groups received asthma treatment following a standardized asthma care path.

All patients were contacted by phone by a research assistant on the 6th day following the emergency department visit. Research assistants were not completely blinded during the study. They were initially blinded to the study group at the start of the phone interviews; however, during the course of the

interview they did ask if the prescription for the second dose of dexamethasone was filled and if the medication was given to the patient. Information collected during the phone interview included additional visits to medical providers (ED, primary care or urgent care) for continued asthma symptoms, information was collected on the reason for visit, whether symptoms continued or worsened, and if additional treatment was needed (scheduled visits and unrelated visits were excluded). School days missed due to asthma exacerbation; length of time symptoms persisted; compliance with the recommended steroid regimen; and any vomiting, side effects or medication administration problems caused by the steroids was also collected.

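### Symptom duration is right-censored at the day-6 call, but the plan analyses it with a t-test that has no place for patients still symptomatic then

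*Combined protocol and SAP*

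**What the plan says.** The Study Protocol section describes one follow-up contact: "All patients were contacted by phone by a research assistant on the 6th day following the emergency department visit". Among the items collected there is "length of time symptoms persisted". No later contact is described.

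The Analytic Plan uses this duration twice. First as a continuous outcome: "Separate independent t-tests were used to assess differences by group for post-discharge outcomes of interest including days for symptoms to resolve". Then in the list of outcomes for the adjusted binary logistic regressions, which reads "days to symptom resolution, any missed school days between discharge and follow-up", with the results given as follows: "odds ratios with 95% confidence intervals were reported". The neighbouring school-days item is already in yes/no form; the symptom item is left as a count of days.

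Neither section gives a value for a patient whose symptoms had not resolved by the call, a censoring rule, a time-to-event method, or a threshold for the day count. The intention-to-treat statement in the Analytic Plan attaches to the comparisons by asthma severity and assigns no value to an unresolved patient.

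**The concern.** A patient still symptomatic on day 6 has a duration known only to exceed about six days. A t-test needs a number for every patient it analyses, so one of two things must happen.

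- **The patient has no resolution day and falls out of the test.** The comparison is then restricted to patients who recovered within six days. That selection depends on the outcome itself and can differ between arms.
- **The patient is recorded as 6.** The comparison is then valid, but it compares mean symptom days within the first six days. It should not be called time to resolution.

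The reader cannot tell which quantity the reported difference measures. In the first case the difference may also be wrong in size, in either direction.

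The logistic model raises a smaller point. A day count cannot be a binary outcome, so it was presumably split somewhere, and the odds ratio cannot be interpreted without knowing where. That is a reporting gap, not a source of bias.

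**Working it through.** **The plan's own figures.** The documents give no mean, SD or unresolved share for symptom duration, so nothing on this outcome can be reproduced. The sample size rests on return visits: 2 × 0.12 × 0.88 × (1.645 + 0.842)² / 0.11² ≈ 108 per group, matching the plan at one-sided alpha 0.05. Symptom duration does not enter it.

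**Illustration: assumptions, not taken from the documents.** Durations follow a Weibull distribution with S(t) = exp(−(t/scale)^shape), rounded up to whole days; anything above 6 is unresolved. Shape is 1.0 or 1.5, the two-dose scale is 3, 4 or 5 days, and the single-dose scale is 1.33 times longer.

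**Formulas.**
- Share unresolved: u = S(6).
- Mean with unresolved patients kept at 6 (six-day restricted mean): K = S(0) + S(1) + … + S(5).
- Mean with unresolved patients dropped: D = (K − 6u) / (1 − u).

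**One setting in full (shape 1.5, scales 3 and 3.99).**
- Two doses: K = 1 + 0.825 + 0.580 + 0.368 + 0.215 + 0.116 = 3.104; u = 0.0591; D = (3.104 − 0.355) / 0.941 = 2.922.
- Single dose: K = 1 + 0.882 + 0.701 + 0.521 + 0.367 + 0.246 = 3.717; u = 0.1582; D = (3.717 − 0.949) / 0.842 = 3.288.
- Difference: 0.61 days kept, 0.37 days dropped, so 60% remains.

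**All six settings.**

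| Shape | Two-dose scale | Unresolved, two / single dose | Difference kept at 6 | Difference dropped | Share left |
|---|---|---|---|---|---|
| 1.0 | 3 | 14% / 22% | 0.46 | 0.21 | 45% |
| 1.0 | 4 | 22% / 32% | 0.43 | 0.17 | 38% |
| 1.0 | 5 | 30% / 41% | 0.40 | 0.14 | 34% |
| 1.5 | 3 | 6% / 16% | 0.61 | 0.37 | 60% |
| 1.5 | 4 | 16% / 30% | 0.57 | 0.27 | 46% |
| 1.5 | 5 | 27% / 42% | 0.50 | 0.20 | 39% |

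In 6,000 simulated trials per setting with 108 per arm (two-sided 0.05), t-test power is about 7-40% with unresolved patients dropped and about 33-77% with them kept at 6.

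**Opposite direction (crossing curves).** Two-dose shape 1, scale 3; single-dose shape 2, scale 3.3; 14% against 4% unresolved.
- Kept at 6: 3.373 − 3.050 = 0.32 days.
- Dropped: (3.373 − 0.220) / 0.963 − (3.050 − 0.812) / 0.865 = 3.27 − 2.59 = 0.68 days.
- Dropping multiplies the difference by 0.68 / 0.32 ≈ 2.1. T-test power is about 90% dropped and 30% kept.

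**Where it does not matter.** With shape 2 and scales 2 and 2.66, 0.0% against 0.6% are unresolved, and dropping gives 0.56 of 0.58 days. With equal arms (scale 4, shape 1.0 or 1.5), both versions reject about 5% of the time.

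**Keeping at 6 is not mean time to resolution.** Under an assumed gamma model (shape 2, means 3 and 4 days, 9% against 20% unresolved), a true difference of 1.00 day becomes 0.66 kept at 6 and 0.36 dropped.

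**Cut-point.** For identical durations, the unadjusted odds ratio for still being symptomatic runs from 1.59 (after day 1) to 2.99 (after day 6) at shape 1.5, scale 3, and from 1.36 to 1.58 at shape 1.0, scale 5.

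**The case against.** **The share unresolved may be trivial.** The texts that hint at persisting symptoms concern return visits: the call asks "whether symptoms continued or worsened" in connection with extra visits, and the analysis counts "patients who had a return visit for unresolved asthma symptoms". A patient can return on day 2 and be well by day 6. The planning assumption of "a rate of 12% return for asthma for each group" is likewise about visits, and is equal in both arms. None of this gives the share symptomatic at the call. This objection stands: censoring is possible by design, but its extent is unknown.

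**The illustrations are invented.** The Weibull parameters and the 1.33 ratio have no source in the documents. That also stands. They show that the handling can matter, not that it did.

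**A stronger reading is tempting.** A reader might infer that dropping unresolved patients always dilutes a difference and so favours the conclusion that one dose is as good as two. The documents do not support this. They do not say that anyone was dropped, and the crossing-curve setting shows the difference can grow. Nor is any non-inferiority margin stated for symptom duration.

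**A t-test capped at 6 is acceptable.** Correct, provided the result is labelled for what it is. Survival methods are one option, not the only one.

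**The text is in the past tense, with enrolment to March 2018, so naming a main analysis now could be post hoc.** This bears on how the fix is reported. It does not rescue an analysis whose estimand cannot be identified.

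**Conclusion.** The concern holds in limited form. The t-test as planned cannot estimate mean time to resolution if any patient is still symptomatic at the call. What it does estimate depends on handling that the documents leave open.

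Under the assumed settings, dropping unresolved patients leaves anything from 34% of the six-day restricted mean difference to about twice that difference. The effect is near zero if almost all resolve by day 6, and there is no bias if the arms share the same durations. If unresolved patients were recorded as 6, a correct label is enough.

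It would go too far to say that the trial's main comparison is compromised: the return-visit analysis and N = 216 do not use this outcome. The missing cut-point is a reporting correction only. Overall this should be corrected, because a better analysis is available from data already collected, but it does not threaten the trial's basis.

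**What to change.** Keep every randomised patient reached at the call, and replace the plain t-test with one named analysis:

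- time to resolution, censored at the day of the call, with Kaplan-Meier curves and a log-rank test; or
- mean symptom days capped at 6, labelled as a six-day restricted mean.

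Report the number unresolved in each arm and how they were counted. If results are already known, say that the choice was made afterwards, or show both analyses.

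In the logistic list, replace the day count with the binary outcome actually modelled, for example symptoms resolved by day 6 (yes/no) in all patients reached, or state the cut-point used.

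The cost is some wording and a little analysis; no new data are needed. There are real downsides. The result is no longer a simple mean time to resolution. Log-rank can lose power if the curves cross (about 5% against about 30% for the capped t-test in the crossing setting above). A yes/no outcome at day 6 says almost nothing if nearly everyone has recovered by then.

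### The only analysis that gives a difference in symptom days is an unadjusted t-test, so prognostic baseline data already collected are not used to sharpen it

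*Combined protocol and SAP*

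**What the plan says.** The Analytic Plan handles time to symptom resolution twice. First: "Separate independent t-tests were used to assess differences by group for post-discharge outcomes of interest including days for symptoms to resolve". No covariates are attached to these tests.

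The next sentence reads: "Separate binary logistic regression adjusting for age, gender and severity of exacerbation were conducted to assess group differences in post-discharge outcomes". Its list of outcomes includes "days to symptom resolution, any missed school days between discharge and follow-up, rates of vomiting, and side-effects". The results of these regressions are to be given as odds ratios with 95% confidence intervals. No confidence interval is promised for a difference in mean days, and no threshold is given for turning days into a yes/no outcome.

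On baseline data, the Study Protocol section says: "Demographic information such as age, gender, race, duration of asthma symptoms, number of previous hospitalizations, and current medication was collected". It also records PAS among the examination findings. No analysis in the plan uses the symptom-duration item.

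On the outcome, the same section says: "All patients were contacted by phone by a research assistant on the 6th day following the emergency department visit". The interview item is summarised as "length of time symptoms persisted".

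The sample size rests on return visits, with "an estimated non-inferiority limit of 11% and a rate of 12% return for asthma for each group". No standard deviation, margin or power is stated for symptom days.

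**The concern.** Children come to the emergency department at different points in an exacerbation and with different severity. If those features predict how long symptoms last, a t-test leaves the variation they cause in the error term. The confidence interval for the group difference is then wider than it need be, and a chance imbalance between groups is not corrected in the point estimate.

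This matters more than usual here because the trial was sized for non-inferiority. With no margin set for symptom days, similarity on that outcome can be judged only from the interval around the difference. A non-significant t-test with a wide interval says little.

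The plan accepts covariate adjustment in principle, since it adjusts the logistic models. It gives none to the comparison made on the scale of days.

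**Working it through.** **1. Which analyses bear on symptom days**

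| Analysis | Covariates | Result on the scale of days? | Uses baseline symptom duration? |
|---|---|---|---|
| Independent t-test | none | yes | no |
| Binary logistic regression | age, gender, severity | no (odds ratio, cut-point not stated) | no |

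So every analysis that yields a difference in days is unadjusted.

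**2. The plan's own sample size**

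Inputs from the Analytic Plan: 12% return in each group, margin 11 points, power 80%, alpha 0.05. With unpooled variance,

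n per group = 2 × 0.12 × 0.88 × (z for alpha + z for power)² / 0.11².

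With one-sided alpha 0.05 this is 0.2112 × (1.645 + 0.842)² / 0.0121 = 107.9, hence 108 per group and 216 in total, as stated. The figure concerns return visits. It is used below only to supply 108 per group.

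**3. What the t-test can detect**

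With 108 per group, two-sided alpha 0.05 and 80% power, the detectable difference is (1.960 + 0.842) × √(2/108) = 2.802 × 0.1361 = 0.381 SD. The documents give no SD in days, so this cannot be converted.

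**4. What adjusting for symptom duration would add**

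Let r be the within-group correlation between baseline symptom duration and symptom days. This is an assumption, as the documents give no value. Adjustment multiplies the residual variance by 1 − r². The interval width and the detectable difference are multiplied by √(1 − r²). The equivalent unadjusted size is 108/(1 − r²) per group. Power is for a true difference of 0.381 SD.

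| r | Variance removed | Interval width factor | Detectable difference (SD) | Power | Equivalent n per group |
|---|---|---|---|---|---|
| 0 | 0% | 1.000 | 0.381 | 80.0% | 108.0 |
| 0.1 | 1% | 0.995 | 0.379 | 80.4% | 109.1 |
| 0.2 | 4% | 0.980 | 0.374 | 81.6% | 112.5 |
| 0.3 | 9% | 0.954 | 0.364 | 83.6% | 118.7 |
| 0.4 | 16% | 0.917 | 0.349 | 86.4% | 128.6 |
| 0.5 | 25% | 0.866 | 0.330 | 89.9% | 144.0 |

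The table assumes a linear model and an outcome observed for every child. It ignores the very small cost of estimating the slope. It does not carry over to a time-to-event model.

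**The case against.** The strongest reply is that an adjusted analysis of this outcome is already planned: the logistic list names it, and severity, which the plan defines by PAS, is among the covariates. A reader who sees only the t-test sentence might infer that symptom days are never adjusted for anything, and the documents contradict that. What stands against the reply is that a day count cannot enter a binary model without a cut-point, and that an odds ratio does not estimate a difference in days.

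The second objection concerns the key covariate. The duration item sits in a list headed as demographic information. Duration of the current episode is the likely reading, but time since asthma began is possible and the text does not settle it. This stands, so the covariate can be recommended only conditionally. PAS, age and gender carry no such doubt.

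Three stronger readings are tempting and should be resisted.

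- **The t-test is biased.** Under randomisation, leaving out a covariate costs precision. The unadjusted interval already allows for chance imbalance.
- **The outcome includes pre-visit days.** The interview item, as summarised, has no starting point, so a reader might infer that caregivers counted from onset. But the script is not in the documents, and the Analytic Plan classes the measure as a post-discharge outcome. The calls have also been made, as the document is in the past tense with enrolment to March 2018.
- **The loss equals dozens of patients.** If covariates explained 10%, 20% or 30% of variance, 216 × (1/(1 − R²) − 1) gives 24, 54 or 93 extra patients. Those R² values have no support in the documents and leave out small ones. For duration alone they would need r of about 0.32 to 0.55 (√0.10 to √0.30). The 216 also belongs to a different endpoint.

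**Conclusion.** The concern holds in a limited form. The comparison of symptom days on its natural scale uses no baseline information, although PAS, age, gender and a symptom-duration item are collected. The consequence is lost precision on an outcome that did not drive the sample size. The return-visit comparison is unaffected.

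The size of the loss cannot be fixed from the documents. For symptom duration alone it is negligible for r up to 0.2, at no more than 4% of variance and under 2 power points. It is moderate for r from 0.3 to 0.5, at 9% to 25% of variance and about 4 to 10 power points. This rests on the assumed r, on the item meaning the current episode before the visit, and on resolution times being known. The last is doubtful for children still symptomatic at the day-6 call. The change is worth making because it costs almost nothing, not because a large gain has been shown.

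**What to change.** Replace the t-test for this outcome with a linear model of symptom days on group, baseline PAS entered as a score, age and gender. State what the baseline symptom-duration item measures, and add it to the model if it means the current episode before the visit. Report the adjusted mean difference with its 95% CI and show the unadjusted difference alongside. If children still symptomatic at the call are handled by a time-to-event analysis, put the same covariates in that model. Choose the covariates without reference to the group results, and if the unadjusted results are already known, say that the adjusted analysis was added afterwards.

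The cost is a little more analysis work. The covariates are already collected (subject to the meaning of the duration item), and no patients, procedures or new data are needed.

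### Return visits are only implied as the primary outcome, and five to seven outcomes, partly repeated in two severity groups, are tested without multiplicity control

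*Combined protocol and SAP*

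**What the plan says.** Everything relevant is in the Analytic Plan, apart from the severity classes and the follow-up call.

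- **Models.** "Separate binary logistic regression adjusting for age, gender and severity of exacerbation were conducted to assess group differences in post-discharge outcomes". The outcomes listed are return visits, time to symptom resolution, any missed school, vomiting, and side effects, with appetite, insomnia and mood given in brackets. Symptom duration is also compared by t-test.
- **Repeats.** "Similar analyses were conducted to compare events and side effects between Groups 1 and 2 by asthma severity". Study Setting and Participants admits two classes, mild (PAS 5 to 7) and moderate (PAS 8 to 11).
- **Reporting.** "odds ratios with 95% confidence intervals were reported", and "All statistical tests were two-tailed".
- **Sample size.** It is based on "an estimated non-inferiority limit of 11% and a rate of 12% return for asthma for each group", and then: "With a power of 80% and alpha of 0.05, a minimum sample size of 216 (108 subjects per group) was determined".

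No outcome is called primary or secondary. No testing order, multiplicity adjustment or exploratory label appears. The text does not say that the return-visit result will be compared with the 11% limit.

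**The concern.** The design and the analysis do not meet. The sample size treats the trial as a non-inferiority question about return visits. The analysis text gives return visits the same two-tailed odds-ratio comparison as, for example, mood swings. Nothing in the plan fixes which result decides the trial.

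The risk runs both ways. A chance tolerability advantage for one dose, or a chance efficacy advantage for two, could be presented with the same standing as the result the trial was sized to give. It matters more here because the trial is un-blinded. The outcomes are also collected by telephone, by assistants who learn during the call whether a second dose was prescribed and taken. The softer outcomes therefore need a clear rank below the lead outcome.

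**Working it through.** **Inputs from the documents.** Return rate 12% in each group, limit 11 percentage points, power 80%, alpha 0.05, 1:1 allocation, 108 per group; two severity classes; the outcomes listed above. The 5% level per test is inferred from the 95% intervals and the stated alpha.

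**Assumed, because the documents do not give them.** All event rates other than 12%, the correlation between outcomes, and the mild/moderate split.

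**1. The plan's own figure.** n per group = (z₁₋α + z₀.₈)² × 2 × 0.12 × 0.88 / 0.11². With one-sided α = 0.05 this is 107.9, so 108 per group and 216 in total, an exact match. With one-sided 0.025 it is 137 per group. The sample size is therefore a non-inferiority calculation on the absolute difference in return visits and on nothing else.

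**2. Count of tests.** Five outcomes if side effects are one outcome, seven if three. The severity repeats cover events and side effects, so symptom duration may or may not be included. The additional t-test of symptom duration is not counted.

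**3. Independent tests.** Chance of at least one false positive = 1 − 0.95^k.
- k = 5: 22.6%
- k = 7: 30.2%
- k = 14: 51.2%
- k = 21: 65.9%

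The last figure is too high for this plan, because each overall test is built from the same patients as its two severity tests.

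**4. Allowing for overlap and correlation.** Take Z_overall = √w·Z_mild + √(1−w)·Z_moderate, where w is the mild share (0.3 and 0.5 tried), with equal correlation between outcomes, 400,000 null draws and |Z| > 1.96.

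| Tests | corr. 0 | corr. 0.3 | corr. 0.5 |
|---|---|---|---|
| 5 overall | 23% | 21% | 18% |
| 5 overall + both severity groups | 45–46% | 42% | 37–38% |
| 7 overall | 30% | 27% | 23% |
| 7 overall + both severity groups | 57–58% | 52–53% | 45–46% |

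**5. Binary outcomes and the planned type of test.** Null trials were simulated with 108 per arm, half mild (54 per arm in each severity group), without covariate adjustment. Correlations were 0 to 0.5, except 0 to 0.4 in the rare-event row.

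| Assumed rates and count | Test | Overall | With severity groups |
|---|---|---|---|
| Seven: return 12%, vomiting 5%, each side effect 20%, school absence 60% | Score (chi-square) | 28–30% | 54–58% |
| Same | Wald on log odds ratio | 25–28% | 46–49% |
| Seven, rare events: return 12%, school absence 50%, vomiting 3%, each side effect 5% | Wald | 20–21% | about 34% |
| Five, side effects as one outcome | Wald | about 19–20% | 35–37% |

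The Wald test is closest to the planned logistic models. It is conservative when events are rare, which is why its figures are lower. The narrowest count, five outcomes overall and four by severity, gives 32–33% with Wald tests if side effects are assumed at 30%.

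**The case against.** Four points on the other side have weight.

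**A lead outcome is implied.** Only return visits have a margin, an assumed rate and power, and they come first in the list of logistic outcomes. A reader might infer from the missing label that no outcome has any priority. The sample size contradicts that. What stands is narrower: the priority is not declared and is not carried into the analysis.

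**A false positive is not shown to be more likely than not.** A reader might infer this from the 51–66% for 14 to 21 independent tests, or from the 54–58% with score tests. The overall tests alone never exceed about 30%. With the Wald tests that fit the planned regressions, every setting examined stayed below one half. Seven is also not a minimum count, since the bracketed side effects can be read as examples of a single outcome.

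**The trial's main decision error is not inflated.** The risk of wrongly declaring non-inferiority on return visits is unaffected by also testing vomiting or mood. This is correct and limits the seriousness of the point. It protects the conclusion only if that comparison is declared to be the one that decides, which the plan does not do.

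**The plan claims nothing for secondary outcomes.** It reports intervals, and the 5% per test is inferred. This is true, but it calls the comparisons tests and does not label any of them exploratory.

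**Conclusion.** The point holds in a limited form and should be corrected; it does not invalidate the trial. Return visits are the implied primary outcome, not the declared one, and they are analysed on the same terms as four to six other outcomes. Those comparisons, partly repeated in two severity groups, have no multiplicity control. With no true difference, at least one p < 0.05 would occur with a probability of about 20–30% over the overall tests and about 34–57% with the severity groups. The narrowest counts fall a point or two below these ranges. Even the lower ends are about four times (20/5) and almost seven times (34/5) the nominal 5%.

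The ranges rest on 108 per arm, half mild, correlation of 0 to 0.5, a 5% level per test, and event rates of which the documents give only the 12%. Where the truth lies within them depends mainly on how side effects are counted, which test is used and how rare the events are.

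**What to change.** Add two sentences to the Analytic Plan.

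1. Return visits by day 6, in all randomised patients, are the single confirmatory outcome, judged against the 11% non-inferiority limit. This means reporting the difference in return proportions with its interval, because an odds ratio is not on the scale of the limit. The level should be stated too: 216 matches a one-sided 5%, and at one-sided 2.5% the power with 108 per group is about 70%.
2. All other outcomes, including vomiting and side effects, and all results by severity are reported as estimates with 95% confidence intervals, labelled secondary or exploratory, with no confirmatory significance claim.

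The plan should also say whether side effects are one outcome or three, and whether symptom duration is included in the severity repeats.

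A formal gate or Holm correction for vomiting and side effects is not recommended, because it could mute a signal of harm. If the data have already been analysed, the report should say that the ranking was set afterwards and rests on the a-priori sample size.

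The change needs no new patients or data. Its cost is that secondary and severity-group differences can no longer be claimed as significant findings.

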### Study Setting and Participants:

Children aged 2 to 20 years with a known history of asthma who presented to the Emergency Department at Women and Children's Hospital of Buffalo/Oishei Children's Hospital between April 2015 and March 2018 with an acute exacerbation of mild or moderate asthma were eligible for the study. Asthma severity was defined by Pediatric Asthma Scores[2, 12] (PAS). Mild asthma is defined as: PAS of 5 to 7; Moderate asthma is defined as: PAS of 8 to 11; Severe asthma is defined as: PAS of 12 or more. History of asthma is defined by physician diagnosis of at least one prior episode of wheezing which responded to beta agonists. Patients were excluded from the study if they had signs of severe asthma exacerbation (PAS of 12 or more), had used oral steroids in the last 2 weeks, had chronic lung disease (e.g., cystic fibrosis), had been given parenteral steroids, or if they vomited two doses of oral steroids in emergency department.

Research assistants screened asthma patients through the electronic medical record between the hours of 8 a.m. and 11 p.m. 7 days a week. Patients were approached sequentially based on registration time. If a patient appeared to meet study criteria, his/her ED treating physician was approached by the research assistant for identifying patient's eligibility. If a patient was fully eligible, the legal guardian and/or patient were approached for consent.

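### School absence is collected as a number of days, but the only named analysis is any versus none; an analysis of the day count should be added

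*Combined protocol and SAP*

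**What the plan says.** The Study Protocol section lists "School days missed due to asthma exacerbation" among the items asked in the telephone call made "on the 6th day following the emergency department visit". This is a number of days.

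The Analytic Plan mentions school absence once, as "any missed school days between discharge and follow-up". It stands in the list governed by "Separate binary logistic regression adjusting for age, gender and severity of exacerbation were conducted", with odds ratios and 95% confidence intervals as the reported effect.

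The plan's other sentence on outcome comparisons reads "Separate independent t-tests were used to assess differences by group for post-discharge outcomes of interest including days for symptoms to resolve". That list is open-ended. It names days to symptom resolution and does not mention days missed from school.

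Both arms receive the same dose in the emergency department. The two-dose arm also receives a prescription for a dose "administered at home 24 hours later".

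**The concern.** Any versus none gives a child who misses one day the same value as a child who misses four. In many trials that is a modest loss. Here the timing of the randomised difference adds to it. A child kept home on the first school day after discharge is already a yes before a second dose given at 24 hours could shorten the illness. Whatever happens to that child afterwards, the recorded outcome is fixed. An earlier return to school in this group would therefore not show in the named analysis.

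At stake is the reading of a secondary outcome that matters to families. If the comparison is insensitive, an absence of difference could be taken as support for a single dose when it reflects the scale used.

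**Working it through.** **The plan's own figure.** The documents give no rate, mean or distribution for school absence. Their sample size concerns return visits: 2 × 0.12 × 0.88 × (1.645 + 0.842)² / 0.11² = 107.9, so 108 per group and 216 in all, with alpha taken as one-sided 0.05. It is used below only as the number per arm. Everything else is an assumption.

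**Step 1: information kept under a common odds ratio.** For an ordered outcome with category probabilities pᵢ, the information about a common log odds ratio is proportional to (1 − Σpᵢ³)/3. For any/none it is proportional to p₀(1 − p₀), where p₀ is the share with no missed day. The efficiency of any/none is therefore 3p₀(1 − p₀)/(1 − Σpᵢ³). The assumed probabilities are for 0, 1, 2, 3 and 4 days. The 30% row scales the non-zero probabilities of the 50% row by 0.6.

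| Share missing a day | Assumed probabilities | Calculation | Efficiency | Loss |
|---|---|---|---|---|
| 30% | .70, .15, .09, .042, .018 | 0.630/0.653 | 0.965 | about 4% |
| 50% | .50, .25, .15, .07, .03 | 0.750/0.856 | 0.88 | 12% |
| 70% | .30, .30, .20, .12, .08 | 0.630/0.936 | 0.67 | 33% |
| 85% | .15, .30, .30, .15, .10 | 0.3825/0.938 | 0.41 | 59% |

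As a cross-check, suppose the counts were Poisson with mean m. Any/none then keeps m·e⁻ᵐ/(1 − e⁻ᵐ) of the information on a log rate ratio: 77% at a mean of 0.5 days, 58% at 1, 43% at 1.5 and 31% at 2. The pattern is the same: little is lost when absence is uncommon, and more than half when it is common and long.

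**Step 2: power with 108 per arm.** These are simulated trials with unadjusted two-sided 5% tests: a two-proportion test on any/none and a Mann-Whitney test on days. With a common odds ratio of 2, and 50%, 70% or 85% of two-dose children missing a day, any/none has power of about 70%, 56% and 36%. The rank test has 80-81% in each case.

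**Step 3: an effect only on days after the first.** Let 70% or 85% of both arms miss day 1. Further days missed follow Binomial(3, 0.25) in one arm and Binomial(3, 0.38) in the other.

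- If only children absent on day 1 can miss later days, any/none has about 5% power, which is the test's own error rate. The rank test has about 38% and 69%.
- If children present on day 1 can also miss later days, any/none rises to about 27% and 14%, against about 86% and 90% for the count. With day-1 absence at 50% or 30%, any/none reaches about 44% and 62%.

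**Step 4: the opposite case.** Suppose the effect is only on whether a child misses any day: a 17-point difference from 30%, 50% or 70%, with each of up to three further days following on with probability 0.2 or 0.5. Any/none then has about 71-88% power and a t-test on days about 47-80%. The rank test is closer, at about 62-87%, between 1 and 11 points below any/none in the same scenario.

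**The case against.** Four objections have force.

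First, a reader might infer that dichotomising throws away most of the information. Only the 85% scenario loses more than half. Enrolment starts at age 2 and screening runs seven days a week, so many children may have few or no school days at risk. The loss could then be only a few per cent.

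Second, a reader might infer that any later effect is hidden. That holds only if children present on day 1 are never absent afterwards. A child whose first absence follows a weekend or a relapse does change the any/none result, and Step 3 shows power of 14% to 62% when this is allowed. The count still does better, but the effect is not invisible.

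Third, the open-ended t-test list means that a comparison of days missed is not ruled out, so it would be wrong to say the plan analyses absence only as any/none. What stands is that no analysis of days is specified. The choice is left open, and a t-test would lack the covariate adjustment used for the binary outcome.

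Fourth, days to symptom resolution already covers duration in part. It does, but recovery and return to school are different outcomes.

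Step 4 also shows that any/none is the better scale for one kind of effect. That is a reason to keep it, not a reason to omit the count.

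**Conclusion.** The concern holds in a limited form. The number of days is collected, any versus none is the only named analysis of absence, and no analysis of the number is specified. Because the arms differ only from 24 hours onward, the named scale can miss a shorter absence among children already absent on the first day.

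The size cannot be fixed from the documents. The range of about 4% to 59% rests on the assumed distributions and a common odds ratio, and the power figures rest on the further assumptions in Steps 2 to 4.

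A reader might go on to infer that this tilts the trial's main conclusion towards the single dose. The documents do not support that. The margin and sample size rest on return visits, and school absence carries no margin or power claim. This is a worthwhile improvement to a secondary analysis.

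**What to change.** Add to the Analytic Plan an analysis of the number of school days missed from discharge to the day-6 call, preferably a proportional-odds regression adjusted for age, gender and severity. Report the difference in mean days with a 95% CI. Keep the any/none odds ratio beside it as an inferential result, not only as a description.

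Limit both to children who attend school. Where available, account for school days at risk, derived from the visit date and the school calendar. The Study Protocol section does not list school attendance among the items collected, so the plan should say how it is determined. Since the text describes a completed trial, an analysis added after the data were seen should be labelled as such.

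The cost is a few sentences, some derivation of days at risk and one more secondary comparison, with no added patient burden. The count analysis has somewhat less power than any/none if the effect is only on whether any day is missed, which is why both should be shown.
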